All SAM children at these 5 sites will be asked to a whole stool sample. For whole stool collection, the caregiver will be provided with a diaper and an adhesive urinary bag to prevent contamination by urine, and asked to wait until the child passes a stool, for a maximum of 4 hours after arrival. When the child passes a stool, the stool will be aliquoted into cryotubes and stored in a cooler bag immediately (within 15 minutes of collection), before being transferred to storage with liquid nitrogen or long-term storage at -80° C within 2 hours of collection. Further details on stool collection procedures are documented in the annexed SOP (see Annex 3).

Fecal samples will be collected at three timepoints: at baseline (initiation of treatment), at discharge from treatment, and at 3-months post-discharge. The baseline sample collection will occur before administration of antibiotics.

Table 7. Study procedures and data collection schedule

	Treatment course													Post-treatment											
	Wk 0*	Wk 1	Wk 2	Wk 3	Wk 4	Wk 5	Wk 6	Wk 7	Wk 8	Wk 9	Wk 10	Wk 11	Wk 12**	Wk 13	Wk 14	Wk 15	Wk 16	Wk 17	Wk 18	Wk 19	Wk 20	Wk 21	Wk 22	Wk 23	Wk 24
Determination of eligibility																									
Informed consent																									
Clinical evaluation***																									
Costing caregiver questions (subset)																									
Anthropometry***																									
Monitoring of adverse events ***																									
Capillary blood collection																									
Stool collection (subset)																									

*Initiation of wasting treatment

**Discharge from wasting treatment (approximately week 12)

***Follow up will be bi-weekly for MAM children and weekly for SAM children in accordance with national guidelines

Data management and confidentiality

Data will be collected by study staff at the study sites using standardized questionnaires and entered by study staff into electronic data capture system (Survey Solutions). Data will be regularly checked by designated staff for quality assurance. This electronic data capture system will be password-protected, secure, and only accessed by qualified study staff. Documents with identifiable information such as consent forms will be stored securely at the study office and accessed only by qualified study staff. All data collection will be directed by SOPs which will be developed and finalized prior to initiation of enrollment.

Statistical analysis

All analyses will be delineated in detail in the trial Statistical Analysis Plan (SAP) which will be developed and finalized prior to initiation of enrollment. A summary is given here.

The study is powered for separate comparisons between (i) the control group and SMS-RUTF, and (ii) between the control group and S-RUTF. All analyses will be stratified by MAM vs SAM status.

Baseline characteristics will be assessed with descriptive statistics (means and standard deviations for continuous variables, and proportions for categorical variables). Baseline characteristics will be adjusted for in the analyses if it is both (i) associated with treatment outcomes or relapse in published literature and (ii) imbalanced between treatment arms as determined by statistically significant t-test or χ^2 tests with 5% significance level.

For binary outcomes, we will use log-binomial regression to estimate relative risks (RRs) and 95% confidence intervals (CIs) for the RRs, adjusting for any baseline factors as appropriate. Non-inferiority will be declared if the lower bound of a one-sided 95% CI for the RR lies entirely below the non-inferiority margin of a relative 12.5%. For continuous outcomes, we will use linear regression to estimate differences in that outcome between treatment arms, adjusting for any baseline factors as appropriate. For superiority analyses (relapse), we will use a two-sided 95% CI and superiority will be declared if the lower bound of the 95% CI for the relative risk is above 1.0.

Non-inferiority analyses can be spuriously favored by ITT analyses because non-compliance diminishes any treatment effects, thus biasing the effect size toward the null (35). We will therefore repeat all non-inferiority analyses with a per-protocol (PP) population, restricting the analyses to only children who comply with their full treatment course, per caregiver report. The ITT and PP results will be presented side-by-side for non-inferiority analyses; superiority analyses will be analyzed as ITT only.

Adverse event (AE) and serious adverse event (SAE) monitoring and reporting

AEs and SAEs will be closely monitored and addressed in both study arms through the routine monitoring of children under wasting treatment, through weekly in-facility visits for SAM children and bi-weekly for MAM, as per national guidelines. AEs/SAEs will be documented in detail and reported to the study leadership. We will ensure the child receives appropriate medical care and monitoring as per guidelines. Definitions of AEs and SAEs are delineated in the annexed SOP (see Annex 4), where procedures are also documented in further detail.

A Data Safety and Monitoring Committee (DSMC) will be formed prior to initiation of enrollment to monitor SAEs, to review the protocol, and evaluate the statistical analysis plan. The DSMC will consist of a professor in pediatrics with experience in child wasting, a professor in epidemiology, and a statistical analysis expert. Monthly AE/SAE summaries will be compiled and sent to the chair of the DSMC. In case of a disproportional rise in monthly SAEs, the chair will convene the DSMC to decide whether the trial should be halted. Given the short character of the trial, there will be no interim analysis.

Early withdrawal from the study

While the study team intends to follow all participants from admission to treatment until 3 months post-discharge from treatment, participants have the option to withdraw from the study at any time for any reason, in accordance with the principles of voluntary participation (outlined in more detail in the section on Ethics below). A participant may be withdrawn from the study by the principal investigator (who will be blinded to treatment allocation) if they believe it is in the participant's best interest to do so. The reason for early withdrawal will be documented in the participant's study file, and if the withdrawal is due to an SAE, prompt medical treatment will be ensured.

Ethics

The study protocol will be submitted for review to the Institutional Review Boards (IRBs) of IFPRI (Washington DC, USA), and the Burkina Faso National Ethics Committee. In accordance with IFPRI requirements, all IFPRI staff participating in the study will have completed the Collaborative Institutional Training Initiative (CITI Program) basic training "Social and Behavioral Research", which addresses research ethics issues in data collection, analysis, and management. The entire data collection team will be trained in, and bound by, the basic ethical principles as outlined in the Declaration of Helsinki (36).

Community engagement

The research team will inform local and regional health authorities and community representatives of the research. In each locality in the study area, representatives of the research team will present the objectives and procedures of the study to the village authorities.

Voluntary and informed participation

The purpose and procedures of the study will be explained to all caregivers of eligible children in their local language through an information sheet. All respondents reserve the right to refuse to participate in the study and to withdraw from the study at any time, for any reason. Each interviewer will be asked to read the consent statement in its entirety, slowly and in the participant's local language so that they can understand it. They will then ask if the consent statement has been understood and if there are any questions. Consent for children will be given by a parent or legal guardian. An informed consent form will be signed by the child's primary caregiver or legal guardian, and, if present, the heads of the household.

Risks and benefits

There are no known risks related to the data collection through questionnaires or anthropometry. The child may feel some pain with the finger prick for capillary blood collection, and there is a slight chance of bruising. There are no direct benefits to the participants for participating in the study. There is an indirect benefit to the participants by the generation of evidence that may serve to benefit the community.

AE/SAE response

In the event of a medical problem (AE/SAE) that occurs or is identified during the assessment visits, all study participants will receive medical care. We will ensure that participants' medical care expenses are covered, whether by the Burkina Faso health care system or by the study insurance.

Participant privacy and confidentiality

Every precaution will be taken to ensure the anonymity of participants during data collection, data management, data analysis and dissemination of results. Completed questionnaires will be stored on a secure server accessible only to the study team. All databases will be made anonymous using identification codes. No personally identifiable data will be shared outside the survey team or kept in the de-identified databases.

Trial registration

The trial will be registered with clinicaltrials.gov and any modifications to the study protocol or consent forms will be submitted for ethical approval before implementation.

Record keeping and Trial Master File (TMF) management

The TMF will be managed electronically by the investigator and investigator-sponsor team, in compliance with the ethical principles outlined above for participant privacy and confidentiality. The electronic TMF will be stored securely, will be password-protected, and will be accessed only by study staff. Prior to enrollment, the investigator and investigator-sponsor team will prepare and keep updated all documents. Written approval of the principal investigator will be obtained before destroying the TMF.

The TMF will include, but not be limited to, the following documentation:

- Approved protocol and any modifications, and all former versions
- Current questionnaire forms
- Insurance policy records
- Signed and dated curriculum vitae of all investigators and study personnel
- Approved informed consent forms in French and English, and all former versions
- SAE reports
- Investigators brochure and certificates of Good Manufacturing Practices for the interventional RUTF products
- Signed SOPs
- Budget details and financial aspects
- Statistical Analysis Plan
- Syntax for data quality checks
- Staff delegation logs
- Communication plan

Dissemination

We will disseminate results from this research in peer-reviewed journals, at scientific conferences, and through stakeholder meetings to relevant study partners.

Timeline summary

The trial is slated to begin enrolling in October 2024, with final follow-up visits occurring in October 2025 (Table 8). Primary analyses will be complete by February 2026.

Table 8. Chronology of the study

	Y1				Y2				Y3
Timeline	Q1	Q2	Q3	Q4	Q1	Q2	Q3	Q4	Q1
Protocol development and ethical review									
Production and shipment of RUTF									
Enrollment									
Recovery from SAM/MAM									
Post-recovery follow up									
Analysis of fecal samples									

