This will be a facility-based, individually randomized, controlled trial with three arms, including two interventions (SMS-RUTF and S-RUTF) and one control arm (standard RUTF), and a 1:1:1 allocation ratio. Children will be enrolled upon initiation of MAM or SAM treatment and followed for 3 months post-discharge from treatment. The national CMAM protocol of Burkina Faso will be followed when evaluating the different RUTFs.

Randomization procedure

A statistician who is not part of the research team will generate a randomization scheme for the allocation of the 3 supplements. Each unique randomization number is randomly allocated to 1 of 9 letter codes (e.g., A, E, I, Z, K, T, N, E, S)—3 letters for the SMS-RUTF supplement, 3 letters for the S-RUTF supplement and 3 letters for the standard RUTF (control group)—using a computer program in permuted blocks of 15. Without notifying the investigators, the statistician will inform the producers which letters to print on the package of each supplement. Information regarding the assignment of the letter codes to the intervention and control supplements is sealed in opaque envelopes, who locked the envelope away until analysis was completed. Before the study started, the clinical research coordinator will seal each of the randomization numbers with the corresponding letter codes of the RUTF supplements into separate opaque envelopes that were marked with unique participant numbers to be attributed at study inclusion. At study inclusion, the study nurse opens the next sealed envelope in the presence of an eligible mother-child pair (in order of arrival) and provides them with the RUTF supplement according to the letter code. The participant's number, as well as the letter code, will be written down on the study participant's card.

Study participants and determination of eligibility

The population for this study will be children 6-59 months old with MAM or uncomplicated SAM presenting to the study facilities. MAM will be defined as middle upper arm circumference (MUAC) ≥ 11.5 and < 12.5 cm, or weight-for-length/height z-score (WLZ/WHZ) ≥ -3 and < -2 . Uncomplicated SAM (i.e., cases of SAM that are eligible for outpatient treatment) will be defined by all the following criteria: (i) MUAC < 11.5 cm or WLZ/WHZ < -3 , (ii) no clinical complications, and (iii) child passes the appetite test (the child eats at least the amount of RUTF required for passing the appetite test as per Burkina Faso national guidelines (12)).

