The inclusion criteria are therefore:

- Age 6-59 months
- MUAC < 12.5 cm, or WLZ/WHZ < -2
- Absence of clinical complications
- Pass the appetite test
- Accompanied by caregiver or legal guardian
- Caregiver or legal guardian consents to participate

Children will be excluded if they meet any of the following criteria:

- Acute malnutrition requiring hospitalization (presence of clinical complications, failure to pass the appetite test, or presence of bilateral pitting edema (12))
- Known allergy to any of the ingredients in the RUTF products
- Already enrolled in MAM or SAM treatment program
- Presence of physical abnormalities that make measurement of anthropometry impossible
- Caregiver has intention to move out of the study area within the next 6 months
- Children referred from in-patient facilities to continue in ambulatory care

Children will be screened for eligibility upon presentation at the study health centers, and will be determined to be eligible upon diagnosis with MAM or uncomplicated SAM. Because treatment coverage is low in Burkina Faso, the project will organize mass screening campaigns in surrounding villages to detect and refer all MAM and SAM cases for treatment. Additionally, the project will strengthen wasting screening at consultations and well-baby vaccination visits at the study health centers to increase coverage of screening and referrals to treatment.

Informed consent

The caregivers or legal guardian of eligible children will undergo the informed consent process. The Information Sheet and Informed Consent form will be read to the caregiver/ legal guardian of the eligible child in their language. The caregiver/ legal guardian will be given opportunities to ask any questions, and his/her comprehension of the form will be confirmed. He/she will sign the consent form if he/she agrees to participate. If the caregiver/ legal guardian is illiterate, a thumbprint will be collected to substitute for a signature.

Study intervention and control arms

Children admitted into MAM or SAM treatment at the study centers will be randomized to one of three RUTF formulations:

- **Standard of care RUTF (control):** composed of milk powder, sugar, vegetable oil, peanut butter, vitamins, and minerals and low in fiber (0.75g per 100g)
- **Alternative, soy-maize-sorghum-RUTF (SMS-RUTF) formulation (intervention 1):** a milk- and peanut-free product with added crystalline amino acids that provide significantly more fiber (5.0g per 100g)

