## Study eligibility and recruitment

### Main trial

The population for this study will be children 6-59 months old with MAM or uncomplicated SAM presenting to the study facilities. MAM will be defined as mid upper arm circumference (MUAC)  $\geq 11.5$  and  $< 12.5$  cm, or weight-for-length/height z-score (WLZ/WHZ)  $\geq -3$  and  $< -2$  and absence of bilateral pitting edema. Uncomplicated SAM (i.e., cases of SAM that are eligible for ambulatory treatment) will be defined by all the following criteria: (i) MUAC  $< 11.5$  cm or WLZ/WHZ  $< -3$ , (ii) no clinical complications, (iii) absence of bilateral pitting edema, and (iv) child passes the appetite test (the child eats at least the amount of RUTF required for passing the appetite test as per Burkina Faso national guidelines (4)).

The inclusion criteria for MAM ambulatory treatment are:

- Age 6-59 months
- $11.5 \text{ cm} \leq \text{MUAC} < 12.5 \text{ cm}$ , or  $-3 \leq \text{WLZ/WHZ} < -2$
- Absence of clinical complications
- Absence of bilateral pitting edema

- Pass the appetite test
- Accompanied by caregiver or legal guardian
- Caregiver or legal guardian consents to participate

The inclusion criteria for SAM ambulatory treatment are:

- Age 6-59 months
- MUAC < 11.5 cm, or WLZ/WHZ < -3
- Absence of clinical complications
- Absence of bilateral pitting edema
- Pass the appetite test
- Accompanied by caregiver or legal guardian
- Caregiver or legal guardian consents to participate

The exclusion criteria for MAM or SAM ambulatory treatment are therefore:

- Acute malnutrition requiring hospitalization (presence of clinical complications, failure to pass the appetite test, or presence of bilateral pitting edema)
- Known allergy to any of the ingredients in the RUTF products
- Already enrolled in MAM or SAM ambulatory treatment program
- Presence of physical abnormalities that make measurement of anthropometry impossible
- Caregiver has intention to move out of the study area within the next 6 months

Children will be screened for eligibility upon presentation at the study health centers, and will be determined to be eligible upon diagnosis with uncomplicated MAM or SAM.

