#### Sub-study 1: Acceptability

This nested sub-study will recruit children with MAM at a sub-set of 5 of the 30 study facilities in the main trial. Inclusion criteria for this sub-study therefore include age 6-59 months, MUAC < 125 mm and  $\geq 115$  mm, or WLZ/WHZ < -2 and  $\geq -3$ , absence of clinical complications, passing the appetite test, accompanied by caregiver or legal guardian, and caregiver consent. Exclusion criteria include presence of SAM, requiring hospitalization, known RUTF ingredient allergies, already enrolled in a MAM or SAM treatment program, physical abnormalities that cause measurement issues, or plans to move away within six months.

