Transfer to inpatient treatment	Referral or admission to hospital for inpatient treatment during the treatment course. As per the Burkina Faso national protocol, children are to be transferred to inpatient care if they meet any of the following criteria: negative appetite test, weight loss for 3 consecutive visits, stagnant weight for 4 consecutive visits if all other social and nutritional reasons have been addressed, onset of clinical condition (edema, fever, hypothermia, severe dehydration, repeated or incessant vomiting, severe respiratory problem, very pale with difficulty breathing, severe malaria,	Non-inferiority

	abscesses or extensive skin lesions, weakness or unconsciousness, convulsions or malaise) (4).	
Non-response to treatment	Any of the following criteria are met: Absence of weight gain after 5 weeks or at the third visit; weight loss for more than 4 weeks in the program or at the second visit; loss of more than 5% of body weight compared to admission weight at any time; or anthropometric recovery criteria not met after 3 months of follow-up in CMAM. Children who are non-responders are referred to inpatient care as per Burkina Faso guidelines.	Non-inferiority
Adherence to treatment services	Caregiver attends the recommended schedule of visits and receive RUTF supply	Non-inferiority
Relapse to SAM	A new episode of SAM (WLZ/WHZ < -3 or MUAC < 115 mm or presence of bilateral pitting edema) within the 3-month period following recovery from the index wasting episode	Superiority
Relapse to MAM	A new episode of MAM (WLZ/WHZ < -2 and $\geq$ -3, or MUAC < 125 mm and $\geq$ 115 mm) within the 3-month period following recovery from the index wasting episode	Superiority
Morbidity signs or diagnoses	Indication of morbidity on health center card	Non-inferiority
Anemia at discharge	Hemoglobin concentration < 105 gram/liter for children 6-23 months of age or < 110 gram/liter for children 24-59 months of age, at discharge	Non-inferiority
Anemia at 3-months post-discharge	Hemoglobin concentration < 105 gram/liter for children 6-23 months of age or < 110 gram/liter for children 24-59 months of age, at 3-months post-discharge	Superiority
Mortality	Death at any time during treatment or during the post-discharge follow-up period	Non-inferiority

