## Statistical methods

We will conduct two separate comparisons between (i) the control group and SMS-RUTF, and (ii) between the control group and S-RUTF. All analyses will be done separately by wasting severity status (MAM vs SAM); that is, all analyses will be conducted and presented among MAM children and among SAM children separately. No adjustments for multiple comparisons will be made.

For binary outcomes, we will use log-binomial regression to estimate relative risks (RRs) and 95% confidence intervals (CIs) for the RRs, adjusting for any baseline factors as appropriate (described further below). If the regression model is adjusted, we will present both crude (unadjusted) and adjusted model results. If the models do not converge, we will use Poisson regression models with robust estimation of standard errors (26) and report which model was used. Non-inferiority will be declared if the lower bound of a one-sided 95% CI for the RR lies entirely below the non-inferiority margin of a relative 12.5%. For superiority analyses, we will use a two-sided 95% CI and superiority will be declared if the lower bound of the 95% CI for the relative risk is above 1.0. All analyses will be adjusted for health center to reflect the stratified randomization (27–29).

For continuous outcomes measured at one timepoint, we will use linear regression to estimate differences in that outcome between treatment arms, adjusting for any baseline factors as appropriate and health center (as explained above). Both unadjusted and adjusted model results will be presented.

For any outcome for which non-inferiority is demonstrated, we will then sequentially test for superiority. In these cases, we will report both non-inferiority and superiority results. The superiority analysis will be considered exploratory, as the study power calculations were based on non-inferiority effect size.

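### MAM and SAM are not defined as mutually exclusive: Relapse to MAM as written counts some SAM relapses, and no main-trial rule places children who meet both definitions at entry

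*Protocol*

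**What the plan says.** **Entry.** The protocol (Study participants and determination of eligibility) defines MAM by "MUAC) ≥ 11.5 and < 12.5 cm, or weight-for-length/height z-score (WLZ/WHZ) ≥ -3 and < -2". The anthropometric part of its SAM definition is "i) MUAC < 11.5 cm or WLZ/WHZ < -3". The SAP (Study eligibility and recruitment, Main trial) turns these into two separate inclusion lists with the same cut-offs, again joined by an or. Neither main-trial MAM definition adds that no SAM criterion may be met. On who decides, the protocol says that children "will be determined to be eligible upon diagnosis with MAM or uncomplicated SAM", and under Study design that "The national CMAM protocol of Burkina Faso will be followed". The guideline's rule for children with discordant measures is not reproduced.

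**Acceptability sub-study.** Here the SAP does separate the classes: "Exclusion criteria include presence of SAM, requiring hospitalization".

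**Relapse.** Protocol Table 3 and SAP Table 1 define Relapse to MAM with the same construction ("A new episode of MAM (WLZ/WHZ < -2 and" at or above -3, or the MUAC band 115 to below 125 mm). Relapse to SAM needs either measure below the SAM cut-off, or edema.

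**Use of the classes.** Under Statistical methods the SAP states that "all analyses will be conducted and presented among MAM children and among SAM children separately"; the protocol likewise stratifies every analysis. Ration tables (Protocol Tables 1 and 2) and visit intervals (Protocol Table 7 footnote) also follow the class. For power, SAP Table 4 takes 88.6% of relapses as MAM, from a cohort in northern Burkina Faso.

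**The concern.** A child whose MUAC falls in one band and whose WHZ falls in the other satisfies both definitions in full. This matters in two places, to different degrees.

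For the relapse-severity outcomes the consequence is direct. An analyst who codes the definitions as printed will count a discordant SAM relapse under both outcomes. Relapse to MAM then stops being a measure of moderate relapse, and an effect of a product on SAM relapse leaks into it. That conflicts with the way the two outcomes were sized.

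For the entry strata the consequence is conditional. The class label fills two enrolment targets of 1080, decides which of two separate analyses a child enters, and selects the margin for some outcomes the SAP ranks as primary (length of stay: 4.9 days for MAM, 8 days for SAM, SAP Table 4). It also fixes visit spacing, and recovery and default are both judged over two consecutive visits. If dual-qualifying children were placed in different classes at different sites, each stratum would describe a less definite population than its name suggests. The SAP's removal of wrongly enrolled children would not detect this, because such a child is eligible under either list.

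**Working it through.** **1. Apply the definitions literally.** MAM if 115 ≤ MUAC < 125 mm or -3 ≤ WHZ < -2. SAM if MUAC < 115 mm or WHZ < -3.

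| MUAC (mm) | WHZ | MAM | SAM |
|---|---|---|---|
| 120 | -3.3 | yes | yes |
| 112 | -2.5 | yes | yes |
| 120 | -2.5 | yes | no |
| 112 | -3.3 | no | yes |
| 120 | -1.0 | yes | no |
| 130 | -3.2 | no | yes |

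The overlap is exactly the discordant group, with one measure in the SAM band and the other in the MAM band. All six children meet the any-wasting definition (MUAC < 125 mm or WHZ < -2) once only.

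**2. The split implied by the SAP.** Inputs: relapse r = 30%, the prevalence scenario in Protocol Table 4 and one of the literature values in SAP Table 4; MAM share 0.886 (SAP Table 4); SAM share taken as the remainder, 1 - 0.886 = 0.114.

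- Relapse to MAM, exclusive: 0.30 × 0.886 = 26.6%
- Relapse to SAM: 0.30 × 0.114 = 3.4%
- Sum: 30.0%, the any-wasting rate

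**3. The same with the printed definitions.** Let f be the fraction of SAM relapses that also meet the MAM definition. The documents do not give f, so the full range 0 to 1 is shown.

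- Relapse to MAM = 0.30 × (0.886 + f × 0.114)
- Sum of the two outcomes = Relapse to MAM + 3.4%

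| f | Relapse to MAM | Relapse to SAM | Sum | Any wasting |
|---|---|---|---|---|
| 0 | 26.6% | 3.4% | 30.0% | 30.0% |
| 0.5 | 28.3% | 3.4% | 31.7% | 30.0% |
| 1 | 30.0% | 3.4% | 33.4% | 30.0% |

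With the 236 children per arm that Protocol Table 4 allows for relapse, the most that can be double counted is 236 × 0.0342 = 8 events per arm, against 236 × 0.2658 = 63 true MAM relapses. The largest relative inflation, 0.114 / 0.886 = 12.9%, does not depend on the relapse rate chosen.

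**4. Entry strata.** No corresponding calculation is possible. It would need the share of children with discordant MUAC and WHZ and the way sites labelled them, and neither document gives either.

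**The case against.** The strongest reply is that the classes are settled in practice. Each child is admitted to one programme on diagnosis, under a national guideline that may contain a precedence rule. The acceptability exclusion and the SAP's split of relapses both show that the authors think of the classes as exclusive. This stands as far as entry is concerned: the omission may be one of wording. It does not help the relapse outcomes, which are the trial's own definitions and will be coded from the text.

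Several stronger readings are tempting, and the documents do not support them.

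- *The strata are contaminated.* Nothing shows that any site classified dual-qualifying children inconsistently. If all sites used one rule, there is no misclassification.
- *The arms are biased.* Class is determined before the allocation envelope is opened, so mislabelling should not differ by arm. The protocol's pooled entry criterion (MUAC < 12.5 cm or WLZ/WHZ < -2) also means that the overlap admits or excludes nobody.
- *A large number of children are affected.* Assuming bivariate normal MUAC and WHZ, one can simulate 33-58% of SAM children as dual-qualifying, or about 360-630 of 1080. Every parameter behind that range is assumed, and it counts children who qualify twice, not children placed wrongly.
- *The main-trial MAM list should simply gain the sub-study's SAM exclusion.* That would settle which ration and visit schedule a child gets, which is a clinical matter. The SAP's account of the product switch also refers to enrolment in the past tense, so the edit would be retroactive. It could trigger the SAP's rule that ineligible children are removed from the analysis.

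**Conclusion.** The overlap is certain from the text. Applied as printed, Relapse to MAM is wrong as a measure of moderate relapse: at 30% relapse it lies between 26.6% and 30.0%, and the two severity outcomes sum to between 30.0% and 33.4%. These figures assume that the SAP's 88.6% is an exclusive share and that the remaining relapses are SAM. The position within each range depends on an unstated discordant share. Relapse to any wasting, which is a primary outcome, does not move, and the recovery definition does not use the split.

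For the entry strata the finding is narrower. The documents state no main-trial rule for children who meet both definitions, although every analysis depends on the label. That is a risk to the description of each population, of unknown size. Severity: should-fix, mainly affecting two secondary outcomes.

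**What to change.** Before the allocation codes are opened:

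1. **Relapse outcomes (Protocol Table 3, SAP Table 1).** Define Relapse to MAM as an episode that meets a MAM criterion and no SAM criterion. Because follow-up is monthly, a child can have MAM at one post-discharge visit and SAM at a later one, so this clause alone does not make the outcomes exclusive per child. State how such a child is counted, for example by worst severity within the 3 months.
2. **Entry classification (SAP, Statistical methods).** State one mutually exclusive classification for analysis. Reconcile the protocol's eligibility section, the SAP's main-trial lists and the acceptability criteria with the ration tables, the visit schedule and the programme each child actually entered. Report the number of dual-qualifying children by arm. Add a sensitivity analysis that reclassifies them from recorded admission MUAC and WHZ. Keep this as a sensitivity analysis, since reclassified children would carry the other programme's ration and visit spacing into their new stratum. Which clinical class governs care is for the sponsor and the national guideline.

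Cost: one derived variable and one extra analysis on data already collected, with slightly fewer Relapse to MAM events (at most about 8 per arm under the assumptions above).
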